10.3 Statistical Analyses and Methods

Continuous variables will be described by using mean values with their respective 95% confidence intervals (CIs); SD; range; 25th, 50th (median), and 75th percentiles; and counts of missing and non-missing values.

The geometric coefficient of variation will be expressed as a percentage for PK and PD data. The geometric mean and its respective 90% CI will be calculated for PK and PD data. The 90% CI for the geometric mean will be calculated by log transforming the data, calculating the lower and upper limits of the 90% CI of the mean of the log-transformed data, and subsequently back transforming the lower and upper limits.

Categorical values will be described using counts and percentages.

All data will be displayed in by-subject listings. The listings will be sorted by treatment arm, study site, subject, time point, and item number (if applicable).

As it is expected that the coronavirus disease 2019 (COVID-19) pandemic is still ongoing during the conduct of the study, it will be assessed for subjects who are affected by COVID-19 during their participation in the study if they will be excluded from some analyses. Reasons for an exclusion will be documented. Adverse events and early discontinuations caused by COVID-19 will be flagged. Protocol deviations caused by COVID-19 will be documented and listed.

A complete description of the statistical analyses and methods will be available in an SAP, which will be finalized before the database is locked.

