4.5 Determination of the Sample Size

In total, 60 subjects are planned to be randomized.

Forty subjects with C1-INH HAE type 1 and type 2 completing the 6-month Treatment Period are needed to achieve a power of approximately 90% for a two-sided Wilcoxon Test (alpha of 5%). Subjects will be randomized to the Active Arm or the Placebo Arm with a ratio of 3:2. An attack rate per month of 0.3125 for CSL312-treated subjects and of 1.3 for subjects receiving placebo are assumed. The monthly attack rates of placebo and of CSL312 are assumed to be Poisson distributed.

The sample size calculation is performed with SAS 9.4 using proc power procedure with twosamplewilcoxon test=WMW which performs power analyses for the Wilcoxon-Test for two independent groups, i.e. the CSL312 and the Placebo treatment in Study CSL312_3001. The Wilcoxon Rank Sum test is testing from departure from the null hypothesis and is assessing if there is a location shift between the distributions of the HAE attack rates of the CSL312 and the Placebo treatment. SAS Proc Power procedure uses the O'Brien-Castelloe approach to compute approximate power. Alpha is set to 5% [O'Brien & Castelloe, 2006]. The assumed monthly attack rates of placebo and of CSL312 (i.e. 1.3 and 0.3125 attacks/month, respectively) are used as the two means of the two Poisson distributions. The randomization ratio of 3:2 was implemented by GROUPNS = (24 16) resulting in a total sample size of 40 which is the lowest one reaching 90% power.

It is targeted to randomize approximately 5 adolescents into the treatment period with a randomization ratio of 3:2 (active:placebo).

To allow for sufficient safety data, to increase the likelihood of adolescents entering the study and, to have at least 40 subjects reaching the end of the study, an additional 20 subjects are planned to be randomized.

In case it is not feasible to randomize the targeted number of adolescents, the targeted total sample size will be achieved by randomizing the needed number with adult subjects.

In addition, it is targeted to include 5 Japanese subjects into the total 60 subjects randomized.

Based on Method 1 and Method 2 in the [Basic principles on Global Clinical Trials] the sample size of the Japanese subjects are planned as below. The point estimate of the endpoint in each arm for Japanese population and other regions (for Method 2) are assumed as the same as that for the global population.

Method 1

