With setting the notations of treatment differences between CSL312 and placebo arm as D, the treatment difference in the global population as D_{all} , and the treatment difference in the Japanese subpopulation as D_{Japan} , the probabilities of $D_{Japan}/ D_{all} > 0.5$ were calculated for the settings that the global sample size is 60 patients (CSL312 arm = 36 patients, and placebo arm = 24 patients) including the Japanese sample size of 5 – 8. The Japanese sample sizes of each arm were rounded based on the 3:2 randomization ratio.

Table 4 Sample Size Justification for Japanese Subjects - Method 1

Japanese sample size			Probability (%) of $D_{Japan}/ D_{all} > 0.5$	
Total	CSL312	Placebo	With median	With mean
5	3	2	64	70
6	4	2	63	71
7	4	3	65	76
8	5	3	73	76

Method 2

With setting the notations of treatment differences between CSL312 and placebo arm as D, the treatment difference in the global population as D_{all} , the treatment difference in the Japanese subpopulation as D_{Japan} and the treatment difference in other regions x as $D_{other-x}$, the probabilities of that all of the global, Japan and other regions of $D > 0$ were calculated for the settings that the global sample size is 60 patients (CSL312 arm = 36 patients, and placebo arm = 24 patients), the Japanese sample size is 5 – 8, the sample size of North America and Europe are assumed to be the same. The sample sizes of each arm for Japan and other regions were rounded up based on 3:2 randomization ratio.

Table 5 Sample Size Justification for Japanese Subjects - Method 2

Sample size for each region			Probability (%) of all of D >0	
Japan	North America*	Europe*	With median	With mean
5	27	28	75	86
6	27	27	73	85
7	26	27	70	91
8	26	26	67	92

* Expected that the sample sizes for North America and Europe would be the same. If not divisible, the sample size of Europe includes one more patients than that of North America.

As the results, if the Japanese sample size is 8, the probabilities to achieve consistency between the Japanese subset and the global population are 67%–92% using mean and median with 3:2 randomization ratio based on Method 1 and 2. Eighty percent probability would be achieved with 5 Japanese patients already when using the mean and Method 2.

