10.2 Subgroup Analyses

If ≥ 5 Japanese subjects are enrolled to the study, the following subgroup analysis will be carried out for Japanese and all subjects:

- Descriptive analysis of the primary endpoint: time-normalized number of HAE attacks per month during the Treatment Period, see [Section 10.1](#);
- Descriptive analysis of the reduction in attack rate during the Treatment Period, see [Section 10.3.2.1](#);
- Descriptive analysis of time-normalized number of HAE attacks requiring on-demand treatment, see [Section 10.3.2.2](#);
- Overview summary of TEAEs, see [Section 11.2](#);

If ≥ 5 Japanese subjects are enrolled to the study, the following subgroup analysis will be carried out for Japanese/non-Japanese subjects:

- Summary for CSL312 concentrations, see [Section 12.1](#).

Summaries for CSL312 concentrations will further be stratified by Age group (adolescent [12 to ≤ 17 years] and adult [>17 years] subjects), see [Section 12.1](#).

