11.4.3 Physical Examination

Date and time of performed physical examinations will be listed only.

12 Pharmacokinetic Analyses

Plasma samples for CSL312 concentrations will be collected during Treatment Period at the following study visits: Day 1, Day 31, Day 61, Day 91, Day 121, Day 151, Day 182 and Day 242 (if applicable).

All analyses in this section will be based on the PK Analysis Set and will be only conducted for subjects treated with CSL312.

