12.1 Drug Concentration Measures

The summaries will be given by nominal time points (planned time points) with descriptive statistics: mean, SD, percent coefficient of variation, median, minimum, maximum, and first and third quartiles for continuous variables, geometric mean and its respective 90% CI.

The geometric coefficient of variation will be expressed as a percentage and will be calculated as $100 * \sqrt{\exp(\text{SD}_{\log}^2) - 1}$. The geometric mean and its 90% CI will be calculated by log-transforming the data, calculating the mean and the lower and upper limits of the 90% Wald CI of the log-transformed data, and subsequently back transforming the mean and the lower and upper limits.

The summaries for CSL312 concentrations will be also stratified according to the following:

- Age (adolescent [12 to ≤ 17 years] and adult [>17 years] subjects),
- Region (Japanese and non-Japanese subjects).

Below lower Limit of Quantification (BLQ) of CSL312 plasma concentrations will be handled as follows:

- pre-dose BLQ results (prior first study drug administration) will be treated as zero;
- all other post-dose BLQ results will be set to missing.

If in total more than 50% of the values at a nominal time point are imputed (i.e., BLQ) or missing, then the summary statistics will not be displayed.

Mean (\pm SD) CSL312 concentrations versus nominal time point will be plotted on linear and semi-logarithmic scales.

All concentrations results will be listed by subject, including actual sampling date and time, nominal time point and actual time from end of previous injection. BLQ results will be listed as "BLQ".

13 Pharmacodynamic and Biomarkers Analyses

All analyses in this section will be based on PD Analysis Set.

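### SAP 12.1 specifies a 90% Wald interval for the CSL312 geometric mean; in the adolescent and Japanese strata, with about 3 treated subjects each, it covers about 76%

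*SAP*

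**What the plan says.** Protocol Section 10.3 describes a 90% CI for geometric means of PK and PD data, obtained by "calculating the lower and upper limits of the 90% CI of the mean of the log-transformed data" and back-transforming. It names no multiplier.

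SAP Section 12.1 keeps these steps for CSL312 concentrations but makes the interval a Wald interval: "calculating the mean and the lower and upper limits of the 90% Wald CI of the log-transformed data".

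The same section extends the tables to subgroups: "The summaries for CSL312 concentrations will be also stratified according to the following", namely adolescents and adults, and Japanese and non-Japanese subjects. SAP Section 10.2 repeats the age split ("Summaries for CSL312 concentrations will further be stratified by Age group") and makes the Japanese split conditional on at least 5 Japanese subjects being enrolled. The opening text of SAP Section 12 says that the PK analyses "will be only conducted for subjects treated with CSL312".

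The group sizes come from SAP Section 4.5. About 5 adolescents are targeted at 3:2, and "it is targeted to include 5 Japanese subjects into the total 60 subjects randomized". Table 4 there splits 5 Japanese subjects into 3 on CSL312 and 2 on placebo, and 8 into 5 and 3.

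SAP Section 12.1 suppresses a summary only when more than half of the values at a time point are imputed or missing. It sets no minimum number of subjects for printing an interval.

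**The concern.** A Wald interval for a mean is the estimate plus or minus a normal quantile times the standard error. It treats the SD as known. With dozens of subjects that is harmless. With three, the SD is itself very uncertain, and the normal quantile makes the interval too short for its label.

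The SAP plans this interval for strata of about that size. What is at stake is the stated precision of the geometric mean exposure in adolescents and Japanese subjects, the two groups with the fewest data. A reader who takes the 90% label at face value would expect the interval to miss the true geometric mean one time in ten, when it would miss it about one time in four.

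**Working it through.** **Inputs**
- Nominal level 90%, two-sided, Wald, log scale (SAP 12.1). Normal multiplier z(0.95) = 1.645.
- Treated subjects per small stratum: 5 × 3/5 = 3 (targets and ratio in SAP 4.5; Table 4 gives the same for Japan).
- Whole active arm: 60 × 3/5 = 36. Adults treated: 36 − 3 = 33. Likewise non-Japanese treated: 36 − 3 = 33.
- Assumed: log concentrations are normal, and the SD is estimated with divisor n−1.

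**Coverage.** The interval is mean ± 1.645 × SD/√n. Because (mean − true mean)/(SD/√n) follows a t-distribution with n−1 degrees of freedom, coverage is 2·F(1.645; n−1) − 1, where F is the t distribution function. I start with the whole arm, where the stated 90% should nearly hold.

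| Treated n | Actual coverage | t multiplier | Log-scale width, t relative to Wald |
|---|---|---|---|
| 36 (whole arm) | 89.1% | 1.690 | 1.03 |
| 33 (adults or non-Japanese) | 89.0% | 1.694 | 1.03 |
| 5 | 82.5% | 2.132 | 1.30 |
| 4 | 80.1% | 2.353 | 1.43 |
| 3 (target) | 75.8% | 2.920 | 1.78 |
| 2 | 65.2% | 6.314 | 3.84 |

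The stated level is therefore reproduced to within about one point in the whole arm, but not in the small strata.

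At n = 3 the formula can be checked by hand: 1.645/√(2 + 1.645²) = 1.645/√4.706 = 1.645/2.169 = 0.758. A simulation of 1,000,000 samples of size 3 gave 75.8% with the normal multiplier and 90.0% with the t multiplier.

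**Size on the concentration scale at n = 3.** The documents give no between-subject CV, so a range is assumed. With SDlog = √ln(1 + CV²), the limits as multiples of the geometric mean are exp(± multiplier × SDlog/√3). At CV 40%, SDlog = √ln 1.16 = 0.385 and SDlog/√3 = 0.222.

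| Assumed geometric CV | Wald limits | t limits |
|---|---|---|
| 20% | 0.83 to 1.21 | 0.72 to 1.40 |
| 40% | 0.69 to 1.44 | 0.52 to 1.91 |
| 60% | 0.59 to 1.69 | 0.39 to 2.55 |

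**Does the display rule help?** With 3 treated subjects and one post-dose value missing or below quantification, 1/3 = 33% are missing. That is below the 50% threshold, so an interval is still printed, on n = 2, with 65.2% coverage.

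**The case against.** The strongest reply is that little depends on this interval. SAP 12.1 calls these descriptive statistics, and no PK hypothesis, equivalence margin or subgroup ratio is tied to them. The four hierarchical hypotheses in SAP 4.2 and 10.5 are all efficacy hypotheses. All of that stands.

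A reader might infer that the interval is the only evidence on adolescent or Japanese exposure. The documents do not support that. The same tables give mean, SD, CV, median, quartiles, minimum and maximum; with three subjects the minimum, median and maximum are the data. Every concentration is listed, and population PK is reported separately (SAP Section 3). Nor would a correct interval on three subjects establish similarity or difference.

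The SAP prints no multiplier, so 1.645 rests on the usual meaning of Wald. If the programmers use a t quantile, coverage is 90% and only the wording is wrong. This is a fair condition on the 76%, but it is no reason to leave the wording.

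The subgroup size is a target. Adolescents form a randomization stratum, but adults replace them if recruitment falls short. Region is not a stratification factor, so 3 treated Japanese subjects is an expectation. The minimum of 5 Japanese subjects counts both arms and does not guarantee any number treated. Eight Japanese subjects would give 5 treated (Table 4), still only 82.5%.

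Two further inferences fail. The first is that the PD intervals share the defect: SAP 13.1 does not specify Wald and summarizes by treatment arm, without age or region strata. The second is that the SAP contradicts the protocol: the protocol leaves the multiplier open, so the SAP has filled a gap, though with a choice unsuited to the small strata.

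**Conclusion.** The point holds as a wrong confidence level in prespecified subgroup tables. At the targeted size of about 3 treated subjects, the interval labelled 90% covers about 76%, and it stays below 83% up to 5 treated subjects. The whole arm, adult and non-Japanese intervals, at about 89%, are close enough to nominal to leave aside.

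This rests on a normal multiplier, log-normal concentrations, an SD with divisor n−1, and the targeted subgroup sizes. With divisor n, coverage at n = 3 would be lower still, at 68.9%. The concentration-scale limits also rest on assumed CVs.

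The consequence is limited to the stated precision of descriptive PK summaries. The primary analysis, the hierarchical tests and the sample size are untouched.

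**What to change.** In SAP 12.1, replace the 90% Wald CI with a 90% CI based on the t-distribution with n−1 degrees of freedom, for the mean of the log-transformed concentrations, then back-transform as planned. This stays within the protocol's description and restores 90% coverage under log-normality at every n.

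The cost is one phrase in the SAP and the matching program line. Log-scale intervals become 1.78 times as wide at n = 3, 1.30 times at n = 5 and about 3% wider for the whole arm. Alternatively, the SAP could omit the interval below a stated minimum number of treated subjects and rely on the range and listings there.

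Using the same t interval for the PD geometric means in SAP 13.1 would be for consistency only.

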13.1 Pharmacodynamic Analyses

Samples for FXII concentrations and FXIIa-mediated kallikrein activity will be collected during Treatment Period at the following study visits: Day 1, Day 31, Day 61, Day 91, Day 121, Day 151, Day 182 and Day 242 (if applicable).

The summaries will be given by nominal time points (planned time points) and by treatment arm with descriptive statistics: mean, SD, percent coefficient of variation, median, minimum, maximum, and first and third quartiles for continuous variables, geometric mean and its respective 90% CI. All PD concentration results will be listed by subject, including actual sampling date and time, nominal time point and actual time from end of previous injection.

Mean (\pm SD) concentration/activity-time profiles will be plotted using nominal (planned) time. FXIIa-mediated kallikrein activity % of Baseline values will also be provided in the listings, summaries, and figures.

BLQ results will not be considered for summaries and will be listed only.

